The clinical tests and scales used in the study are all routinely included in the clinical assessment of patients with cognitive disorders. The only exception is the CGI, which is not an actual test, but simply a scale for semi-quantified rating of treatment response based on the existing knowledge of the patient. A regular blood test is carried out to determine serum concentrations and genetic analysis. The methods for serum concentration analysis and genetic analysis are described in the introduction to the protocol. Clinical symptoms and the results from the tests and scales used will be systematically recorded in the CRF, as will

information on co-morbidity, use of other medications, occurrence of side effects and treatment compliance.

Focus group interviews with relatives

When we assess the effect of a drug or the lack thereof, it is important not only to keep an eye on the purely biomedical causal relationships. In order to nuance the debate, it is relevant to analyze the experiences of the relatives in relation to the medication of the patient with Alzheimer's disease. This can lead to greater insights into what challenges might be present in relation to whether the drug is ingested as prescribed by the physician and whether it has the desired effect.

Purpose: To describe relatives' perspective on treatment with anti-dementia medication in a Danish memory clinic. Method: a qualitative sub-study to gain insights and understanding of what challenges the relatives experience in connection with the patient's medication. The approach is phenomenological and hermeneutically inspired by Paul Ricour's philosophy of narratives (19), where openness to what the relative experiences (lifeworld) is essential.

Participants: 15 relatives who are cohabiting spouses are included in the study. In qualitative research, 15 participants provide rich data (20). The participants are selected in collaboration with the Regional Knowledge Center for Dementia's team based on consideration of which relatives are able to reflect and express themselves on the subject. Qualitative research aims for the greatest possible variation in the sampling of informants (20), which is why the selection is made on the basis of differences in age, gender/relationship to the patient.

Data collection for the qualitative study

Data is produced and collected using focus group interviews. 3 focus group interviews are planned with 5 participants in each group. The size of the focus group can vary from 3-12 participants (21). A group of 5 participants will provide the opportunity to process the material in depth and uncover the relatives' attitudes and social negotiations during the interview. A group with more participants can be more difficult to moderate as an interviewer. During the interview, the interviewer must focus on being open, listening and appreciative, while at the same time being aware that all participants get the opportunity to

express themselves and be heard (21). The data collection is carried out using an interview guide (see appendix) with inspiration from Kvale and Brinkmann (22). The interview guide contains questions that can encourage the relatives to give rich descriptions of the problems and challenges. The interview guide is pilot tested before the 3 focus group interviews. Because of the interview guide, the interviews are structured by open questions related to the topic and thus not "free narration". The interviews are conducted in a conference room in the Neurological Outpatient Clinic in an undisturbed room.

Data analysis:

The relative interviews are transcribed, after which they are included in a Ricouer-inspired analysis and interpretation (19). The analysis is divided into three levels: the naive interpretation, the structural analysis and the critical interpretation. This takes place by first reading through the text material several times, where a comprehensive understanding is achieved. The text is then structured based on units of meaning, from which overarching themes are extracted. The structural analysis takes place in a dialectical process between explanation and understanding. Finally, the critical interpretation is carried out by comparing and discussing the themes found with existing relevant research literature.

Monitoring treatment compliance

Assessment of treatment compliance is carried out according to the memory clinic's general clinical practice. This consists of participants and especially their relatives being interviewed by a physician and contact nurse at follow-up visits about whether the medication has been ingested regularly during the previous treatment period. If the medication is not ingested regularly as prescribed, this is included in the clinical assessment of effect and possibly side effects, and noted in the medical record. In the context of the study, this practice will be followed, i.e. the assessment is carried out at the control visits after ½ and 1 year of treatment. It will also be noted in the CRF whether the drug is ingested either "completely regularly", "regularly with less than 10 missed daily doses in 6 months", "less regularly, with more than 30 missed daily doses in 6 months" or "irregularly with more than 60 missed daily doses in 6 months".

Endpoints for the prospective study

Primary endpoint

When a participant has attended the 1-year follow-up visit the study participation is completed for that individual. When the last participant (as based on the power calculation) has attended the 1-year follow-up visit quantitative data collection for the study will be complete.

Quantitative outcome variables explored in the study

- MMSE
- ACE
- DAD
- CGI
- NPI
- serum concentrations [of either Donepezil or Memantine]
- Genetic variants (liver enzymes, APOE, BchE-K/K)
- Sex
- comorbidity registration
- compliance registration
- EEG

Statistics and power calculation

Several studies and meta-analyses have shown that the clinical effect of anti-dementia drugs can be detected for at least one year after initiation of treatment (23). The effect generally consists of a delay in the development of symptoms corresponding to 2 points on an MMSE scale after one year. We define optimized clinical effect as a decrease of less than 2 points on the MMSE scale in one year. This means that all participants whose score decreases 2 or more points in a year have a sub-optimal clinical effect, while participants whose score has a decrease of less than 2 points in a year has optimal clinical effect. It is emphasized that, as in general clinical practice, emphasis is not placed solely on the change in MMSE score when the effect is assessed. The assessment is based on an overall clinical assessment, where the CGI score is deemed suitable.

Based on clinical database information, 15-20 newly referred patients eligible for study participation will likely be referred to RVD per month. If it is assumed that approx. half will participate in the project, approx. 100 patients could be included in one year.

If it is assumed that <50% of the participants reach the recommended serum concentration and thus relevant clinical effect on standard dosing (cf. pilot study), and that this can be increased to 75% by dose adjustment after S concentration determination, the following calculation can be performed on the basis of the formula:

$$N > (Z_{2\alpha} + Z_{\beta})^2 \times (P_1(1-P_1) + P_2(1-P_2)) / (P_1 - P_2)^2$$

where N is the number of necessary participants in each group, α is significance level 5%, β is the probability of type 2 error (strength is $1-\beta = 80\%$), P_1 is dose optimization (optimized clinical effect) with regular dosing, P_2 is dose optimization (optimized clinical effect) guided by S-level and possibly side effects.

$$N > (1.96+0.84)^2 \times (0.5 \times 0.5 + 0.75 \times 0.25) / 0.25^2 = 7.84 \times (0.25 + 0.1875) / 0.0625 \sim 55$$

In other words, 110 participants must be included in the project period in order to calculate the clinical utility of serum concentration measurements with the stated assumptions. Realistically this goal for participant recruitment can be reached within a study period of one to two years.

Risk assessment (risks and discomfort)

Blood test

For all participants in the study a single blood sample is collected for genetic analyses. For the intervention group, as stated, a single blood sample is also taken in case of side effects, and after $\frac{1}{2}$ and 1 year. The blood sample is collected in a completely routine manner by a trained professional. The procedure is not associated with any other discomfort or inconvenience, apart from what is known for a routine blood test in a normal clinical context. For the control group, a blood sample is collected at the 1 year follow-up visit, when the CRF is closed for that participant.

MMSE, ACE, GDS, DAD, NPI

These are simple and commonly used cognitive tests/scales, which are not associated with any kind of discomfort or discomfort for the subject (MMSE, ACE) or the relative (DAD, NPI). It can be slightly discomforting for a patient to be confronted with his or her cognitive deficits during a test, but the listed tests are all part of the clinical routine at RVD. In total, it will take a maximum of 30 minutes to perform the MMSE and ACE, and roughly the same time to interview the relative for DAD and NPI.

Side Effects and Adverse Events

As by custom in ordinary clinical practice [in RVD], all patients and relatives are informed about potential side effects at the start of treatment and dose adjustments. Side effects are routinely reported to the contact nurse by telephone, in practice this happens on the same day or within a few days after side effects occur. In connection with the project, participants in the intervention group will receive the same information about side effects as in routine clinical practice, supplemented by corresponding information about the need to report by telephone to the contact nurse in the event of side effects. Furthermore, all participants are asked about side effects at the ½-year and 1-year follow-up visits. In each individual case, an assessment will be made by one of the clinic's specialists (senior physicians) as to whether side effects should lead to dose reduction or discontinuation. All reported side effects are entered into the participant's CRF. As by clinical routine, all participants and relatives will be encouraged to contact the contact nurse by telephone in case of any suspicion of side effects. If the reported side effects are deemed to be related to the medicine, common practice is to either switch to an alternative anti-dementia drug or reduce the dose. It depends on a medical assessment whether there is a basis for changing the preparation or reducing the dose. In all such cases, in connection with the project, a blood test will be offered to determine the serum concentration. Common side effects (in 1-10% of subjects): Less than 5% of patients who have a blood test will develop a minor hematoma at the insertion site [of the needle]. This side effect is benign and will disappear without any treatment. Slight pain at the injection site itself and subsequent mild soreness may occur. It may occur that participants who are uptitrated in dose on the basis of low serum concentrations will develop side effects. These are mainly mild gastrointestinal side effects, and in rare cases cardiac side effects. Occurrence

of such potential side effects will be closely monitored and the clinic will immediately respond accordingly. Apart from the time consumption of the cognitive tests and interviews, there are no other known side effects of these studies. There are no side effects or significant risks when recording standard EEG with modified photo-block. The participants can at any time during the EEG recording refuse to complete this study, which must then be complied with by the person in charge of the experiment. In this context, an adverse event (AE) is defined as: any adverse event in a patient or subject in a clinical trial after treatment with a medicinal product, without necessarily having a connection between this treatment and the adverse event.

Registration of unwanted events

All of the following information is recorded by the physician in charge of the study for each adverse event:

- Complete description of the unwanted event.
- Date and time of onset.
- Date and time of resolution.
- The severity of the incident must be assessed by the physician responsible for the study [primary investigator] according to the definitions below.
- Whether or not it is a serious incident.
- Whether the incident was expected or not.
- The relationship to the procedure, which must be assessed by the physician responsible for the study according to the definitions below.
- Action taken (if applicable).
- Result and information for all further follow-ups. Definitions of adverse event severity.

The following are the only definitions used to describe the severity of adverse events:

- Mild – The adverse event does not interfere with the subject's daily routine. It causes slight discomfort.
- Moderate – The adverse event interferes with some aspects of the subject's daily routine.
- Severe – The adverse event causes an inability to perform the subject's daily routine. Only one definition of severity is used for each adverse event (eg a statement such as "mild/moderate" is not acceptable). Moderate or serious adverse events are considered very unlikely in the present project.

Serious adverse events

A serious adverse event (SAE) is understood in this context as all medical occurrences, such as:

- results in death,
- is life-threatening,
- requires hospitalization or extension of an existing hospital stay, results in permanent or significant disability, or inability to work.

Adverse events that meet all of the following criteria:

- Unexpected (i.e. inconsistent with common knowledge about potential side effects)
- There is at least a reasonable possibility that there is a causal connection between the incident and the procedure will be classified as Suspected Unexpected Serious Adverse Reactions (SUSAR).

The assessment of the relationship between an adverse event and the procedure (probable, possible, unlikely, none, cannot be assessed) is a clinical decision based on all available information. Factors that should be considered in the relationship assessment include the temporal sequence from the time of the procedure, improvement upon cessation (withdrawal) of the procedure, underlying concurrent competing illnesses, concurrent medical procedures or treatment, known pattern of response to methods used, exposure to physical and/or psychological stress. The physician in charge of the study, senior doctor [consultant] [name], is responsible for evaluating whether an adverse event

is serious or not and, in case of doubt, relevant information will be obtained and reported in detail. The product summaries for Donepezil and Memantine are used to assess whether a serious related side effect is expected. All adverse events in connection with the experiment will be registered and reported, cf. legislation, to the authorities. The sponsor is required to ensure that all information about SUSARs, which are fatal or life-threatening, is registered and reported to the Danish Medicines Agency as soon as possible and no later than 7 days after the sponsor has become aware of such a suspected side effect. No later than 8 days after the report, the sponsor must notify the Danish Medicines Agency of all relevant information about the sponsor's and investigator's follow-up to the report. All other SUSARs must be reported to the Danish Medicines Agency no later than 15 days after the sponsor has become aware of them.

Monitoring subjects with adverse events

All adverse events that occur during the study must be monitored and followed until they have either resolved, returned to normal or baseline values, reached clinical stability, or been shown to be unrelated to the project.

Ethical considerations

The Study will be conducted in accordance with the Helsinki Declaration of 1984, modified at the 41st World Congress in Hong Kong 1989. The study has been approved by the local Scientific Ethics Committee (SJ-596) and the Danish Data Protection Agency. Participants will only be included after full written and verbal information and provision of informed written consent. Participants can withdraw from the study at any time without reason, and without this affecting any future treatment. Only participants who are deemed to be able to understand the information and independently consent to study participation are included. This also applies to patients with moderate to severe dementia. It may happen that, in connection with the blood sampling and dose regulation (up-adjustment), inappropriate side effects appear temporarily, mainly in the form of gastro-intestinal discomfort (indigestion, abdominal pain, loose stools) and heart rhythm disturbances. Should this occur, the project manager will arrange for an immediate dose reduction and, if cardiac problems are suspected, for an emergency ECG to be taken. Depending on the nature and severity of the

discomfort, an appropriate medical response is given. It may also happen that a participant in the intervention group shows signs of unusual worsening of their dementia at the ½ or 1-year visit. Here, it is the responsibility of the project manager to screen the patient for co-morbidity (possibly in collaboration with his or her GP), and to ensure that the participant is offered combination treatment (AchE inhibitor + Memantine), especially if the S-value of the current treatment is at the recommended level. The participant continues regardless of this in the protocol (if it occurs at the ½-year visit), unless he or she express a wish to withdraw from the study. In addition to determining serum concentrations, the blood samples are used for genetic analysis of variants of liver enzymes [cyp2D6], APOE and BchE-K/K. Participants or relatives do not get specific feedback on the results of these analyses, which will only be used to assess the genetic variation in the population, as well as its significance in relation to the metabolism of anti-dementia drugs. It is our opinion that the expected disadvantages, discomfort and risks for study participants are small and do not outweigh the importance of the expected results.

Approval and monitoring by external authorities

In accordance with current regulations, the protocol was approval by the Regional Scientific Ethics Committee for Region Zealand and the Danish Data Protection Agency [Datatilsynet]. The project was approved by the Danish Medicines Agency and registered at www.clinicaltrials.gov. It will also be monitored externally by the GCP unit at Copenhagen University Hospital.

Insurance

All complaints during the study or possible damage to the test subjects will be handled in accordance with the Danish law on access to complaints and compensation within the healthcare system. The subjects are covered by the [Danish] Patient Insurance [Danish: 'Patientforsikringen'].

Time schedule

The first participant was recruited on 12 February 2020. The last participant was recruited on 24 February 2022. Completion of the last trial participant is expected to take place in early/mid March 2023. Apart from extended participant recruitment, the project is progressing at the time of writing (19 April 2022), according to plan without deviations from current protocol.

Publication and storage of data and biological material.

Blood samples used to measure the serum concentrations are destroyed by the laboratory immediately after the analyses. This applies to all blood samples taken - no biological material is stored or used in a biobank, the blood samples are destroyed immediately after the stated analyzes have been carried out. The Act on the processing of personal data will be complied with. All data will be handled confidentially and published in anonymized form. Raw data and randomization codes will be stored in anonymized form under secure conditions for 15 years after the end of the trial. Study results will be submitted to recognized international journals and both positive and negative results will be published.

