Systematic observations are carried out regarding treatment compliance in both control and intervention groups. In addition, an electroencephalography (EEG) examination is carried out at the baseline visit and after 12 months in 30 participants. After the 12-month visit, a qualitative study is conducted. This study will collect data by interviewing spouses of participants. After the end of the study, the utility of serum determinations of anti-dementia drugs in relation to side effects and clinical efficacy is assessed by comparing the scores of participants in the control and intervention groups for the aforementioned clinical scales.

Project initiator, sponsor, responsible physician and contact person:

[name], senior physician, MD, PhD

Department of Neurology Zealand University Hospital (SUH) [name]
[name] Denmark

Aims of the study

- Investigate whether determination of serum concentration, and regulation of the dose on the basis hereof, improve the clinical treatment response – including whether insufficient clinical effect could be due to too low a serum concentration
- Investigate whether early development of side effects during treatment with anti-dementia drugs is due to too high a serum concentration (ie. serum concentrations above the therapeutic reference range).
- Characterize the proportion of participants who reach a serum concentration within the recommended therapeutic reference range when treated with standard dosages of anti-dementia drugs.
- Study whether the recommended therapeutic reference ranges are valid in relation to clinical efficacy
- Investigate the relationship between serum concentrations and clinical efficacy in different stages of the dementia disease
- Investigate whether measurements of serum concentrations improve treatment compliance, both in relation to side effects and in relation to clinical efficacy
 - Investigate whether sex differences impact serum concentrations, which potentially may have an impact on optimal drug dosing.
 - Investigate whether genetic variation of the metabolism of anti-dementia drugs, impact serum concentration and thus potentially may be important for optimal dosing. With regards to this, analysis of the APOE genotype and analysis of the BchE-K/K variant will be carried out.
- Describe aspects of treatment compliance in in a Danish memory clinic

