A clinical test which, compared to the MMSE, is not routinely used in all clinics, but especially in clinics with a special function, as well as in connection with research projects. The test is a 100-point scale, where points from the MMSE are included in the total score, the higher the score, the better the function. Compared to the MMSE, the test goes into all cognitive domains in more detail and is less language dependent. Healthy people will, depending on age and education, generally score above 85 points. The test can be completed by a trained professional in 10-15 minutes.

Neuropsychiatric Inventory Questionnaire (NPI-Q) (13)

A clinical scale to assess the presence and severity of neuropsychiatric symptoms in dementia. This results in an NPI score (0-36), which is based on an interview with the next of kin [relative]. The higher the score, the more pronounced neuropsychiatric symptoms.

Disability Assessment for Dementia (DAD) (14)

A scale for assessing ADL [Activities of Daily Living] functions (eating, personal hygiene, dressing, etc.), which is based on an interview with next of kin. With completely normal ADL functions, a score of 40 points is achieved, the higher the score, the better the function.

Clinical Global Impression (CGI) (15)

A "global" scale, which is commonly used in clinical trials. This is a 7-step scale by which the clinician grades his overall impression of treatment response. The scale was used in the previously mentioned recent study of plasma concentrations and clinical response. The scale will be weighted, rather than weighted on MMSE scores alone, when assessing treatment response.

Geriatric Depression Scale (GDS)

A scale for assessing severity of depressive symptoms in the elderly. Based on the total point score (0-15), the result is categorized as either "normal" (< 5 points), "possible depression" (5-7 points), "probably mild to moderately severe depression" (8-10), "moderately severe" to "severe depression" (11-12 points), "severe depression" (≥ 13 points).

Compliance Definition:

Compliance means the patient's degree of compliance with the doctor's prescriptions. The term is used especially in drug treatment. Most often, the patient takes less medicine than prescribed. "Non-compliance" typically means that the patient takes < 80% of the prescribed doses. Low compliance can be intentional or unintentional (16).

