tests, partly for serum concentration determination. They are also informed that they will receive at least 1 year of follow-up in RVD, against the usual ½ year. At the visit after 1 year, the same clinical tests and scales are carried out as during the patients' preliminary examination, and matters relating to compliance are queried. The other group (intervention group) will have an extra blood sample taken if they experience side effects from the treatment within the first 2 months. Everyone also has one extra blood test at each The ½- and 1-year check-ups. In addition, they will also be followed for at least 1 year against the normal ½ year. At the 1-year check-up, the same clinical tests and scales are carried out as in the pre-examination, and matters relating to compliance are queried. Subsequently, the respective compliance, distribution of serum concentrations, as well as the importance of serum concentration determination and derived dose regulation for the overall clinical response after 1 year (assessed on MMSE, ACE, NPI, DAD and CGI). A comparison is made of the occurrence, duration and outcome of side effects in the 2 groups, including the proportion of patients who had to change preparations or abandon medical treatment due to side effects. The project manager (alternatively the person performing the test) is blinded in relation to which group the patient is randomized to and to the result of serum values. The final statistical analysis of the clinical value of serum determinations and derivative monitoring is performed by an independent statistician. No participants will receive any form of remuneration for participation in the project. Any additional costs for transport are covered according to the appendix. Use of journal information Journal information is used to identify the target group, including clarifying inclusion and exclusion criteria (see these). During the project period of one year, the journal is used to document and monitor any side effects or unintended events, just as all possible side effects or unwanted events are entered into the patient's CRF.

FLOWCHART FOR PROJECT "MONANTI"

Inclusion criteria for participants

- All patients [evaluated at RVD] who after diagnostic assessment has been completed, meet the criteria for
- Alzheimer's Dementia (AD), (NIA-AA, (1)), Dementia with Lewy-Bodies (DLB) (15) or Parkinson's Disease Dementia (PDD) (18), and
- who are scheduled for treated with Donepezil or Memantine and

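### The primary-endpoint section names no outcome, so the 5% significance level is attached to no declared comparison

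*Combined protocol and SAP*

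**What the plan says.** Endpoints for the prospective study, Primary endpoint, consists of two sentences. The first is "When a participant has attended the 1-year follow-up visit the study participation is completed for that individual"; the second says when data collection for the whole study is complete. A list of eleven unranked variables follows, in which clinical scales stand beside covariates such as sex and genetic variants.

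Statistics and power calculation gives the only operational definition of a clinical outcome: "We define optimized clinical effect as a decrease of less than 2 points on the MMSE scale in one year". The same term labels P1 and P2 in a two-proportion formula (5% level, 1.96, 80% power, 55 per group, 110 in total). The section then qualifies the definition: "emphasis is not placed solely on the change in MMSE score when the effect is assessed", and "The assessment is based on an overall clinical assessment, where the CGI score is deemed suitable".

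The description of the CGI adds: "The scale will be weighted, rather than weighted on MMSE scores alone, when assessing treatment response". Recruitment describes the overall response after one year as "assessed on MMSE, ACE, NPI, DAD and CGI". The Introduction says that the value of serum determinations will be judged by "comparing the scores of participants in the control and intervention groups for the aforementioned clinical scales".

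The planning rates are introduced with: "If it is assumed that <50% of the participants reach the recommended serum concentration and thus relevant clinical effect on standard dosing". They cite the pilot described in Background, in which 8 of 24 serum samples were in range.

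**The concern.** A confirmatory comparison needs one named result that decides it, fixed before the data are seen. Here the section meant to name it deals with another matter, and the rest of the document points in three directions: an MMSE rule with a cut-off, a CGI or overall judgement without one, and a set of five scales without a ranking. Two analysts could both follow this plan on the same data and reach opposite conclusions. An independent, blinded statistician does not remove the problem, because nothing tells that person which outcome counts.

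At stake is the meaning of the 5% level and of the 80% power, since neither belongs to a declared outcome. A smaller point goes with it: the power statement carries a serum-attainment rate over to a clinical response rate.

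**Working it through.** **The plan's own figure.** Inputs from Statistics and power calculation: P1 = 0.50, P2 = 0.75, z-values 1.96 and 0.84.

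N = (1.96 + 0.84)² × (0.50×0.50 + 0.75×0.25) / 0.25² = 7.84 × 0.4375 / 0.0625 = 54.88, so 55 per group and 110 in total. The arithmetic reproduces.

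**What each section would make decisive.**

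| Section | Outcome | Cut-off or rule | Declared primary? |
|---|---|---|---|
| Primary endpoint | none | none | heading only |
| Statistics and power calculation, definition and formula | MMSE fall of less than 2 points in one year | yes | no |
| Statistics and power calculation, following sentences | overall assessment, CGI | none | no |
| Clinical Global Impression | CGI given weight besides MMSE | no weights | no |
| Introduction; Recruitment | MMSE, ACE, NPI, DAD, CGI | no ranking | no |

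Only the MMSE rule has a scale, a cut-off and an interval, and only that rule is tied to the formula.

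**Error rate if the choice stays open (illustration).** Assume k two-sided 5% z-tests with common correlation r (not given in the documents) and no true effect. With Z standard normal, the chance of at least one significant result is

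1 − E[{Φ((1.96 − √r·Z)/√(1−r)) − Φ((−1.96 − √r·Z)/√(1−r))}^k].

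| Scales that could carry the result | r = 0.3 | r = 0.5 | r = 0.7 | r = 0.9 |
|---|---|---|---|---|
| Five | – | 18.3% | 14.8% | 10.2% |
| Two (MMSE, CGI) | 9.5% | 9.1% | 8.4% | 7.0% |

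**Power of a named test.** Exact binomial enumeration at 50% vs 75% with 55 per group gives 80.2% for the unpooled z-test that matches the formula, 78.9% for Pearson chi-square without continuity correction, and 72.1% for Fisher's exact test. Exact type I error of Pearson at common rates of 0.5, 0.625 and 0.75 is 4.5%, 5.2% and 5.0%.

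**What the power statement is conditional on.** Let q be control attainment of the serum range, 75% the intervention attainment, and a and b the response rates in and out of range (assumed). Then P1 = q·a + (1−q)·b and P2 = 0.75a + 0.25b. Unpooled power at 55 per group:

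| a / b | q = 1/3 (pilot) | q = 0.50 (formula) |
|---|---|---|
| 0.9 / 0.1 | 36.7% vs 70.0%, power 96% | 50% vs 70%, power 59% |
| 0.8 / 0.2 | 40.0% vs 65.0%, power 77% | 50% vs 65%, power 36% |
| 0.7 / 0.3 | 43.3% vs 60.0%, power 43% | 50% vs 60%, power 18% |
| 0.9 / 0.3 | 50.0% vs 75.0%, power 80% | not needed here |

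The exact 95% interval for 8/24 is 16% to 55%, treating the 24 samples as independent, so the pilot excludes neither value of q. The results lie on both sides of 80%.

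**The case against.** The strongest reply is that the MMSE rule is plainly the intended primary outcome: it is defined with a cut-off and it labels both proportions in the formula. That supports choosing it in the fix. It does not close the gap, because the sentences directly after the definition take away its exclusive role and no sentence declares it decisive. It is also fair to say that choosing MMSE is a choice, since the protocol gives weight to the CGI as well.

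A reader might infer that the trial's error rate is really 10% to 18%. The documents do not support that: no section plans five tests at 5%, the correlations are assumed, and Recruitment can be read as describing one overall response. The Introduction is the firmer basis for scale-by-scale comparisons.

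A reader might also infer that the trial is underpowered, or that 80% power needs a perfect link between serum level and response. Neither follows. The sample-size text presents its rates openly as assumptions. The 0.9/0.3 case reaches 80% with an imperfect link. The model also treats all out-of-range samples alike, although 6 of the 16 were above range, and it leaves out benefit through side effects, compliance or a change of drug. The pilot covered donepezil only.

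Two further points stand. Naming a scale and a test is not enough without an analysis set and a rule for missing 1-year scores, because the withdrawal criteria remove participants who change to an unmeasured drug while the intervention allows a change of drug. And the finding concerns this document only; the registry entry was not available.

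**Conclusion.** The concern holds, and it needs correcting before the trial's result is interpreted. The text under Primary endpoint names no outcome, the implied MMSE responder comparison is never declared primary, and other sections point to a CGI judgement without a cut-off or to five unranked scales. In this document the 5% level is attached to no declared outcome.

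The size can only be illustrated: about 10% to 18% family-wise error if any of the five scales could carry the result (correlations 0.9 to 0.5), and about 7% to 9.5% for MMSE or CGI only (0.9 to 0.3). These figures rest on assumed equal correlations and on selection that the plan permits but does not prescribe.

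The planning rates are a minor, accompanying matter. The sample-size arithmetic is right for 50% vs 75%; what needs saying is that these must be MMSE-responder rates, whereas the cited pilot supplies only a serum rate.

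**What to change.** Replace the primary-endpoint text with, in substance: the proportion of all randomised participants whose MMSE falls by less than 2 points from the pre-treatment test to the 1-year visit, intervention versus control, by Pearson chi-square test without continuity correction at two-sided 5%. Add a stated rule for missing 1-year scores. Identify which pre-treatment test is the baseline, because Study design places the tests before enrolment while Study execution and visits mentions the preliminary examination or the enrolment visit.

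In Statistics and power calculation and in the CGI description, state that the CGI or an overall judgement does not redefine this outcome in the analysis. Label CGI, ACE, DAD and NPI-Q secondary. Add one sentence to the sample-size text: 80% power at 55 per group holds if 50% and 75% are MMSE-responder rates.

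The cost is wording only, with no new data, visits or participants. Recruitment ended on 24 February 2022, so the power condition can be disclosed but not met by a larger sample. There are two downsides: one scale is chosen although the protocol also values the CGI, and the named test has 79% rather than 80% exact power at the planning rates. The choice must be fixed before the analysis is unblinded; if that has already happened, it must be reported as post hoc.
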